### 2.2.1 Subgroup Definitions

There are no subgroup analyses planned for this study.

## 2.3 Missing Data Conventions

With the exceptions noted below, no missing value imputation will be used. That is, all analyses will be based on the observed data (i.e., complete case analysis).

Missing 24-hour Holter rhythm data will be imputed from 12-lead ECG results for the corresponding visit at 3, 6, and 12 months. Statistics will be computed for complete case analysis and with the imputed data present.

In case of missing data for dates, January will be imputed for missing months and the first will be imputed for missing days for purposes of elapsed time computations.

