### **11.4 Subject Study Completion and Withdrawal**

A subject will be considered completed when the twelve- (12) month visit is completed and all data collection is complete. Subjects who withdraw for any reason will have all available data entered into the database. Reasons for withdrawal will be entered on the Study Completion eCRF.

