### **11.5 Subjects Lost-to-Follow-Up**

A subject will be considered lost-to-follow-up from the last missed clinical evaluation if all reasonable efforts made to contact the subject and request their continued participation in the study have failed. All attempts to contact the subject will be documented.

Whenever possible, subjects who have been withdrawn for reasons other than lost-to-follow-up will be contacted and requested to participate in ongoing safety data assessments, which will be conducted by phone.

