### 5.2.2 Analysis of Secondary Effectiveness Objectives

All secondary effectiveness analyses will be conducted on the treatment population.

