#### Clinical Outcome Measures

The number and proportion of subjects with freedom from documented episodes of AF/AT/AFL lasting longer than 30 seconds, based on the 24-hour continuous ECG monitor at three, six, nine, and 12 months post ablation will be displayed, along with exact binomial 95% CI's for each proportion. Separate proportions and confidence intervals will be calculated for:

- Freedom from AF/AT/AFL with a single procedure
- Freedom from AF/AT/AFL with a single procedure without AADs
- Freedom from AF/AT/AFL with a single procedure with AADs
- Freedom from AF/AT/AFL with multiple procedures
- Freedom from AF/AT/AFL with multiple procedures without AADs
- Freedom from AF/AT/AFL with multiple procedures with AADs.
- Freedom from AF with a single procedure
- Freedom from AF with a single procedure without AADs
- Freedom from AF with a single procedure with AADs
- Freedom from AF with multiple procedures
- Freedom from AF with multiple procedures without AADs
- Freedom from AF with multiple procedures with AADs.

Descriptive statistics (mean, standard deviation, median, range, and number of non-missing responses) on the raw and change from baseline (CFB) LA size will be reported

at 12 months, along with a separate set of descriptive statistics for the raw baseline data. A 95% CI on the mean will also be provided.

The number of repeat ablation procedures in follow-up period from day 91-270 (i.e., from three months to nine months) will be summarized via mean, standard deviation, median, range, and number of non-missing responses. A 95% CI on the mean will also be provided.

The number of DCCV in first 90 days post-ablation and the number of DCCV from day 91-365 (i.e., from three months to 12 months) will be summarized via mean, standard deviation, median, range, and number of non-missing responses. A 95% CI on the mean will also be provided.

Raw and CFB scores for the AFEQT questionnaire will be computed and summarized with descriptive statistics (mean, standard deviation, median, range, and number of non-missing responses) by time point (one, three, six, and 12 months post ablation). The overall AFEQT score is calculated according the following formula:

$$AFEQT_{\text{Overall}} = 100 \times \left( 1 - \frac{\sum A_j - n}{6n} \right),$$

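### The SAP has no rule that keeps a recorded post-blanking recurrence in the 12-month freedom proportion once the subject leaves, so freedom is overstated if leavers have failed more often than stayers

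*Combined protocol and SAP*

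**What the plan says.** SAP 2.3 sets the default: "With the exceptions noted below, no missing value imputation will be used", and "all analyses will be based on the observed data (i.e., complete case analysis"). For rhythm there is one exception: "Missing 24-hour Holter rhythm data will be imputed from 12-lead ECG results for the corresponding visit at 3, 6, and 12 months". Results are to be shown with and without that substitution.

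SAP 5.2.2 (Clinical Outcome Measures) reports "The number and proportion of subjects with freedom from documented episodes of AF/AT/AFL lasting longer than 30 seconds" from the continuous monitor at 3, 6, 9 and 12 months, each with an exact binomial interval, in single-procedure and multiple-procedure rows. On the population it says: "All secondary effectiveness analyses will be conducted on the treatment population". It does not say how a treated subject who leaves is counted at later time points.

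Protocol 11.4 says: "Subjects who withdraw for any reason will have all available data entered into the database". Protocol 7.5 has recurrences beyond the 90-day blanking period recorded on the eCRF. SAP 6.1 tabulates withdrawals and their reasons. No section carries a recurrence forward, counts death, withdrawal or loss as failure, or names a censoring method for this outcome. The time-to-event formula in SAP 3.0 belongs to the baseline summaries.

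**The concern.** A subject whose 6- or 9-month monitor showed AF and who then leaves has no 12-month monitor and no 12-month ECG. Under the default rule that subject is in neither the numerator nor the denominator at 12 months, although the study itself recorded the recurrence and holds it in the database. The ECG substitution cannot help, because it needs the visit to have taken place, and it does not exist at 9 months.

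Efficacy at 6 and 12 months is part of the stated objective (protocol 6.1, SAP 1.0). Protocol 5.2 considers setting treatment success beside historical controls from the literature. With one arm, informative dropout has no comparator in which it might cancel. Both planned versions leave out the same subjects, and the withdrawal table gives reasons but not rhythm status, so a reader of the results could not see the effect.

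**Working it through.** **The plan's own figure.** The only sample-size figure is for the safety endpoint (SAP 1.3, protocol 8.4): 125 subjects, 96.0% free of MAEs, half-width 3.89%. It reproduces. For 120/125 the Clopper-Pearson interval is 90.91% to 98.69%, half-width 3.888%. It does not bear on this point, because the documents state no dropout rate, attrition allowance or expected freedom rate. All counts below except 125 are therefore assumptions.

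**Notation.** N = treated; m = leavers before 12 months; g = leavers with no recorded recurrence; x = completers who are free. Freedom is taken as cumulative after blanking, in the single-procedure rows.

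**Assumed example.** N = 125, m = 15 (10 after a recorded post-blanking recurrence, so g = 5), x = 77.

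- Complete case: x/(N − m) = 77/110 = 70.0%.
- Full follow-up, if all 5 unknown leavers fail: 77/125 = 61.6%.
- Full follow-up, if all 5 stay free: (77 + 5)/125 = 82/125 = 65.6%.
- Excess of complete case: 70.0 − 65.6 = 4.4 points, to 70.0 − 61.6 = 8.4 points.

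**When the bias vanishes.** Take N = 125 with 75 free under full follow-up (60.0%). Let 25 leave at the cohort failure rate: 10 after recurrence, and 15 who stay free. Completers free: 75 − 15 = 60. Complete case: 60/100 = 60.0%, equal to full follow-up.

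**Dependence on who leaves** (same 60.0% full-follow-up value, about 80% of leavers failed, the others staying free):

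| Leave | Of these, failed | Complete case | Excess over 60.0% |
|---|---|---|---|
| 6 | 5 | 74/119 = 62.2% | 2.2 points |
| 12 | 10 | 73/113 = 64.6% | 4.6 points |
| 25 | 20 | 70/100 = 70.0% | 10.0 points |

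Over 50% to 70% freedom, 5% to 20% leaving, and a failure share among leavers from the cohort's own share up to 100%, the difference from full follow-up runs from −0.6 points (rounding to whole subjects) to 17.6 points.

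**Why not simply keep the known failures and exclude the other leavers?** That estimate is x/(N − g). In the case with no bias it gives 60/(125 − 15) = 60/110 = 54.5%, which is 5.5 points too low. Censoring at the time of leaving instead credits recurrence-free leavers with the follow-up they had. In the first example there are (110 − 77) + 10 = 43 recorded failures and 5 censored subjects. Kaplan-Meier then gives 77/120 = 64.2% if all 5 are censored together before any failure, and 82/125 = 65.6% if they are censored after all failures. In the no-bias case the same two extremes are 54.5% and 60.0%, so exclusion is the extreme in which these leavers contributed no follow-up at all.

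**The case against.** The strongest objection is that SAP 5.2.2 never says whether freedom is visit-specific or cumulative. On a cumulative reading an AF episode at 6 or 9 months is itself observed data, and a complete-case rule need not discard it. The table shells that might settle the numerator and denominator are not in the text available. This stands: the defect is an unstated rule with complete case as the default, not a documented decision to discard known failures.

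A reader might infer that 12-month freedom must rise as failures leave. The documents do not support that. Complete case exceeds an estimate that keeps known failures whenever any leaver had a recorded recurrence, but it exceeds the full-follow-up value only if leavers have failed more often than stayers. Nothing shows that they would: protocol 7.5 manages recurrence within the study, and protocol 6.5 follows treatment subjects for its full duration. Leaving because of recurrence is plausible, not documented.

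A reader might also infer that withdrawn subjects are never asked about rhythm. Protocol 11.5 says only that they are "requested to participate in ongoing safety data assessments, which will be conducted by phone"; it does not list the questions, and the call does not cover subjects lost to follow-up.

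A carry-forward rule applied everywhere would clash with the multiple-procedure rows, since protocol 7.5 allows one retreatment between day 91 and day 270. This also stands, and limits the rule.

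Finally, these outcomes are secondary and descriptive, SAP 2.1 excludes hypothesis tests, and protocol 5.2 hedges the historical comparison. That lowers the stakes. Counts per time point and withdrawal reasons would make attrition visible, but not whether those who left had already failed.

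**Conclusion.** The point holds as a gap in definition with a possible upward bias. By default, a recorded post-blanking recurrence drops out of later proportions when the subject leaves, and neither planned version reveals it. The size cannot be taken from the documents. It is 4.4 to 8.4 points under the assumed 125, 15, 10 and 77, and about zero if leavers fail at the cohort rate. These figures rest on cumulative freedom, on the assumed counts, and on the 5 leavers without recurrence being wholly unknown. A claim of certain inflation, or of a known size, would go beyond the documents. The change is worth making because the recurrence data are already collected.

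**What to change.** In SAP 2.3 and 5.2.2:

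- Define the single-procedure rows as cumulative freedom after the 90-day blanking period, with a recorded post-blanking recurrence kept as a failure at all later time points.
- Estimate freedom at 6, 9 and 12 months by Kaplan-Meier or life table, censoring subjects who leave without recurrence, rather than by excluding only those leavers. This assumes that such leaving is unrelated to later recurrence; the sensitivity row below tests it.
- In the multiple-procedure rows, do not carry forward a recurrence that preceded a retreatment the protocol allows.
- Show the denominator at each time point.
- Add one sensitivity row counting all non-completers (withdrawn, lost, died) as not free.

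Questions on recurrence, AAD use and repeat procedures in the protocol 11.5 phone contact would be useful but are optional; the fix does not depend on them.

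The cost is some SAP wording, a little more analysis work and possibly less favourable secondary rates. The 24-hour primary safety result does not change.

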## 5 INTRODUCTION TO THE CLINICAL INVESTIGATIONAL PLAN

### 5.1 Background

Atrial fibrillation (AF) is among the most prevalent arrhythmias in the world today affecting approximately 1.5-2% of the general population. The age of patients with AF is steadily rising and now averages between 75 and 85 years of age. AF is associated with a five-fold risk of stroke, a three-fold incidence of congestive heart failure, and higher mortality.

Symptoms arise from the rapid, irregular rhythm as well as the loss of cardiac pump function related to uncoordinated atrial contractions. These uncoordinated contractions also allow blood to pool in the atria and may ultimately lead to thromboembolism and stroke.

AF is characterized by a chaotic contraction of the atrium in which an electrocardiogram (ECG) recording is necessary to diagnose the arrhythmia. Any arrhythmia that has the ECG characteristics of AF and lasts sufficiently long for a 12-lead ECG to be recorded, or at least 30 seconds on a rhythm strip, should be considered an AF episode.

The diagnosis requires an ECG or rhythm strip demonstrating: (1) Irregular RR intervals (in the absence of complete AV block), (2) no distinct P waves on the surface ECG, and (3) an atrial cycle length (when visible) that is usually variable and less than 200 milliseconds.

AF can be characterized into four classifications:

- Paroxysmal AF (PAF) is defined as recurrent AF ( $\geq$ two episodes) that terminates spontaneously within seven days.
- Persistent AF is defined as recurrent AF that is sustained for seven days. In addition, patients with continuous AF who undergo cardioversion within seven days should be classified as having paroxysmal AF if the cardioversion is performed within 48 hours of AF onset, and persistent AF if the cardioversion is performed more than 48 hours after AF onset.

---

 Camm AJ, et al. 2012 focused update of the ESC Guidelines for the management of atrial fibrillation: an update of the 2010 ESC Guidelines for the management of atrial fibrillation--developed with the special contribution of the European Heart Rhythm Association. *Europace*, 2012 Oct; 14(10):1385-413

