**STATKING Clinical Services**

## Revision History

### Version 1.1 to 2.0

1. Listing 6 (AEs): modified to add columns specifying device relationship to AE for each device.
2. Listing 15 (Catheter Data): Part 5 header corrected. Part 4 Sheath Model number and Lot number added.
3. Listing 16 (PVI Data): Column added to identify visit and PVI count.
4. Table 2 and Time-to-event specification: TTE defined as  $TTE = \text{End-Date} - \text{Start-Date}$  rather than  $\text{End-Date} - \text{Start-Date} + 1$ .
5. Tables 7 and 35: Footnote added to state data source as continuous monitor data with 12 lead imputation when continuous monitor data are unavailable.
6. Table 16: Highest Relationship to Device expanded to summarize relationships to System, Catheter, Sheath, and PEK (in accord with added tables 20- 22).
7. Tables 16, 17, 18, 19 (AEs): Table sources modified to use CEC adjudication only, titles changed to reflect this. Text of Section 4.2.2 changed to reflect these changes.
8. Table 19 (AE Relationship to Device) – Changed to Relationship to AcQMap Catheter.
9. Tables 20-22 – Added to summarize additional AE relationship assessments.

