#### 5.1.2 Description of Secondary Effectiveness Objectives

Secondary measurable effectiveness objectives include the following, which are divided into procedure outcome measures and clinical outcome measures.

The **procedure outcome measures** are:

- Proportion of subjects with acute procedural (ablation) success defined as:
  - Conversion to sinus rhythm (with or without direct current cardioversion [DCCV]) within 12 hours of the procedure
  - Procedural conversion to atrial flutter, atrial tachycardia or other organized supraventricular rhythm
- Procedure fluoroscopy time
- Ablation time to complete PVI
- Ablation time for non-PVI ablation
- Ablation time for right atrial ablation
- Number of DCCV completed during the procedure

The **clinical outcome measures** are:

- Proportion of subjects with freedom from documented episodes of AF/AT/AFL lasting longer than 30 seconds, based on the 24-hour continuous ECG monitor at three, six, nine, and 12 months post ablation. Analysis will include:
  - Freedom from AF/AT/AFL without AADs
  - Freedom from AF/AT/AFL with AADs
  - Freedom from AF/AT/AFL with a single procedure
  - Freedom from AF/AT/AFL with multiple procedures
- Improvement of left atrial (LA) size at 12 months compared to baseline
- Number of repeat ablation procedures in follow-up period from day 91-270 (i.e., from three months to nine months)
- Number of DCCV in first 90 days post-ablation
- Number of DCCV from day 91-365 (i.e., from three months to 12 months)
- Changes in patient reported outcomes (PROs) in the follow-up period, based on the AFEQT questionnaire

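### Filling a missing 24-hour monitor from the visit's 12-lead ECG lets a sinus tracing count as 24 hours free of arrhythmia, and the SAP does not say whether the filled or the monitor-only freedom rate is the main result

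*Combined protocol and SAP*

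**What the plan says.** - **Outcome.** SAP 5.1.2 defines the clinical outcome as freedom from documented AF/AT/AFL episodes "lasting longer than 30 seconds, based on the 24-hour continuous ECG monitor at three, six, nine, and 12 months post ablation". SAP 5.2.2 repeats this and gives each proportion an exact binomial 95% interval.
- **Missing data.** The default in SAP 2.3 is "With the exceptions noted below, no missing value imputation will be used". The exception is "Missing 24-hour Holter rhythm data will be imputed from 12-lead ECG results for the corresponding visit at 3, 6, and 12 months". The next sentence adds: "Statistics will be computed for complete case analysis and with the imputed data present".
- **Tables.** The version 2.0 entry in the SAP revision history says that Tables 7 and 35 gained a footnote stating their "data source as continuous monitor data with 12 lead imputation when continuous monitor data are unavailable". The version 1.1 entry identifies Table 7 as the AF/AT/AFL freedom table. Table 35 appears to be its AF-only companion: version 1.1 introduced that as Table 32, and version 2.0 added three tables (20 to 22) ahead of it. The table shells are not in the supplied text.
- **What a 12-lead ECG establishes.** Protocol 5.1 treats an arrhythmia with the ECG features of AF that "lasts sufficiently long for a 12-lead ECG to be recorded, or at least 30 seconds on a rhythm strip" as an AF episode. Protocol 7.5 also accepts an ECG as documentation of recurrence. Neither document makes a matching statement for a tracing in sinus rhythm.
- **Nine months.** There is no clinic visit (Protocol 7.4.3) and no 12-lead ECG (SAP 4.2.2), so the default of no imputation applies.
- **Three months.** Protocol 6.2.2 and 7.4.3 and SAP 1.2 and 5.1.2 call for a monitor at 3 months. The monitor row in both protocol schedules (Tables 1 and 2) is marked only at 6, 9 and 12 months.

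**The concern.** A 12-lead ECG samples the rhythm at one moment, while the outcome concerns any episode over 30 seconds in 24 hours. Arrhythmia on the ECG supports scoring a failure. Sinus rhythm on it does not support scoring a success, yet the rule substitutes the ECG in both directions. A subject with intermittent arrhythmia and no monitor can therefore be counted as free.

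Two further effects follow. ECG-only subjects enter the exact interval as if fully observed, which narrows it. And the time points in one table rest on different instruments: monitor or ECG at 3, 6 and 12 months, monitor alone at 9.

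At stake is the freedom rate itself. Protocol 5.2 names freedom from AF at 6 and 12 months as treatment success and foresees setting it against published historical controls. The synopsis allows publication at both times.

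**Working it through.** **The plan's own figure.** The documents give no expected freedom rate, missing-monitor rate or precision for this outcome. The only design calculation, a 3.89% half-width for the primary safety proportion, reproduces: 120/125 gives a Clopper-Pearson interval of 90.91% to 98.69%, half-width 3.888%. It does not bear on this point.

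**Inputs (all assumptions).**
- m: share of monitors missing and filled from an ECG
- p: freedom in monitored subjects
- q: true 24-hour freedom in subjects without a monitor
- s: chance that the visit ECG shows the arrhythmia in a subject whose monitor would have been positive
- An ECG showing arrhythmia is taken as a correct failure.

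**Formulas.**
- True rate = (1 − m)p + mq
- Filled rate = (1 − m)p + m[q + (1 − q)(1 − s)]
- Filled minus true = m(1 − q)(1 − s), never negative
- Filled minus complete case = m[q + (1 − q)(1 − s) − p], either sign

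**Excess over the true rate, in points, with q = 70%.**

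| m | s = 0.3 | s = 0.5 | s = 0.7 | s = 0.9 |
|---|---|---|---|---|
| 10% | 2.1 | 1.5 | 0.9 | 0.3 |
| 20% | 4.2 | 3.0 | 1.8 | 0.6 |
| 30% | 6.3 | 4.5 | 2.7 | 0.9 |

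For example, 0.20 × 0.30 × 0.70 = 4.2 points.

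**Effect on the interval.** Take 125 subjects, m = 20%, p = q = 70%, s = 0.5.
- Complete case: 70/100 = 70.0%, interval 60.02% to 78.76%, width 18.74 points.
- Filled: of the 25 without a monitor, 17.5 + 7.5 × 0.5 = 21.25, rounded to 21, are scored free. That gives 91/125 = 72.8%, interval 64.12% to 80.37%, width 16.25 points.

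**When subjects without a monitor do worse.** Take p = 70%, m = 20%. The last column counts every subject without a monitor as a failure: 0.80 × 70% = 56.0%.

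| q | s | True | Filled | Complete case | Missing as failure |
|---|---|---|---|---|---|
| 70% | 0.5 | 70.0% | 73.0% | 70.0% | 56.0% |
| 50% | 0.7 | 66.0% | 69.0% | 70.0% | 56.0% |
| 30% | 0.9 | 62.0% | 63.4% | 70.0% | 56.0% |

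The filled rate exceeds the true rate in every row. In the last two rows it is nonetheless closer to the truth than complete case.

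**The case against.** **The ECG-free result is already planned.** This stands. SAP 2.3 requires complete-case statistics, and the version 1.1 log splits the rhythm table into 12-lead, Holter and post-imputation parts. A reader might infer that the plan reports only the filled rate; the documents do not support that. What is left is that the supplied text names neither result as main, while the table footnote points to the filled source. The log does not say that the freedom tables lack the complete-case version, and without the shells this cannot be settled.

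**Filling may do less harm than leaving out.** This also stands. A reader might infer that the filled rate always exceeds the complete-case rate, or that 9 months is unbiased and a dip there would be an artefact. Neither follows. Nine months is free only of ECG-substitution error. If missed monitors relate to rhythm, complete case is biased there too, and the 9-month value could sit too high.

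**A monitor-only analysis drops known failures.** It leaves out subjects whose visit ECG shows arrhythmia, which Protocol 5.1 and 7.5 would count. This is a fair cost of that choice, and the reason for a bound beside it.

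**The stakes are modest.** The endpoint is secondary and descriptive, and SAP 2.1 plans no tests. Protocol 5.2 claims only that a historical comparison may be informative, and the supplied SAP text specifies none. In the 125-subject example, the bias of about 3 points lies well inside the interval.

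**Conclusion.** The concern holds in a limited form. Followed as written, SAP 2.3 scores some subjects as free on evidence that cannot show it. Against true 24-hour status the filled rate can only be too high, provided that an ECG showing arrhythmia is a correct failure. With q = 70% and s = 0.3 to 0.9, the excess is 0.3 to 2.1 points at m = 10% and 0.6 to 4.2 at m = 20%. These sizes rest wholly on assumed values.

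The rule affects 3, 6 and 12 months. Three months may be the most exposed, because sites that follow the schedule tables would have no monitor to record then. The documents do not show that this will happen. The filled intervals are somewhat too narrow, and 9 months is not on the same basis as the other time points. No hypothesis test or error rate is affected, so this is an improvement the SAP should make, not a defect in the primary analysis.

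**What to change.** In SAP 2.3 and in Tables 7 and 35:

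1. Name recorded 24-hour monitors as the main analysis at 3, 6, 9 and 12 months, in line with the SAP's own outcome definition in 5.1.2 and 5.2.2.
2. Show the ECG-filled result only as a labelled sensitivity analysis.
3. Add a bound at all four time points in which subjects without a monitor count as failures, including those whose ECG shows AF/AT/AFL. This covers both selective missingness and ECG-documented failures left out of the main analysis.
4. Report, for each time point, the number of monitors recorded and the number of subjects filled from an ECG.
5. Reconcile the 3-month monitor between the protocol and SAP text, which require it, and the schedule tables, which do not mark it.

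The cost is SAP wording and a few table rows; items 1 to 4 need no new data. Intervals for the main result will be wider than for the filled result, and reported freedom may move in either direction.
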